2 SYNOPSIS OF STUDY

Phase 1, Double-Blind, Placebo-Controlled			
Assessment of Potential Interactions			
Between Intravenous Cocaine and			
Clavulanic Acid			
CLAV and Cocaine Interaction Safety Study			
Phase Ib			
This is a prospective, placebo controlled			
inpatient crossover safety study of 3 doses (250			
mg/day, 500 mg/day, 750 mg/day) of CLAV			
with an intravenous infusion of cocaine 40 mg.			
Subjects will be non-treatment seeking			
experienced cocaine dependent adults, ages 18-			
65 (N=12 completers, 21 estimated to enroll).			
Subjects will undergo a washout of the study			
drug for 5 half-lives between study drug			
administration sessions.			
Approximately 1.5 years.			
Temple Episcopal Hospital. Centennial 6 th			
floor, an inpatient medical unit with telemetry.			
To determine whether there are clinically			
significant adverse interactions between CLAV			
(250 mg/day; 500 mg/day; 750 mg/day) and			
intravenously administered cocaine in healthy,			
non-treatment seeking adults with cocaine use			
disorder.			
1. To evaluate whether administration of			
CLAV alters the pharmacokinetics (PK) of			
cocaine or its major metabolite,			
benzoylecgonine (BE).			
2. To determine PK of CLAV during treatment			
at 250 mg/day (low dose) and 500 mg/day			
(medium dose).			
3. To evaluate whether there are significant			
interactions between CLAV treatment			
concurrent with i.v. cocaine infusions of 40 mg			
by measuring the diameter of the pupil using a			
pupillometer.			
3. To evaluate whether CLAV treatment alters			
the subjective effects of cocaine, the perceived			
value of the dose of cocaine, and craving.			
4. To assess the effects of clavulanic acid on			
mood and personality and on the abuse			

	liability.		
Outcome Measures	Primary outcome measure is safety which will		
	be measured by AEs, BP, HR, and ECG QTc		
	interval. Secondary outcome measures include		
	PK parameters of cocaine, PK parameters of		
	CLAV, pupillometry. Exploratory outcome		
	measures are subjective effects measurements		
	assessed for cocaine in combination with		
	CLAV and CLAV alone. Effect on mood		
	(POMS), abuse liability (ARCI), and subjective		
	effects measurements (VAQ, VAS) will be		
	obtained. The effect of CLAV on cocaine		
	craving will be assessed using the CCQ-Brief.		
	The DVQ will be used to determine the		
	perceived value of each dose of cocaine.		
Number of Participants	12 completers, 21 estimated to enroll.		
Diagnosis and Main Inclusion Criteria	Non-treatment seeking adults with cocaine use		
	disorder, moderate to severe, ages 18-65.		
Study Product, Dose, Route, Regimen	Clavulanic acid 250 mg/day (always given		
	before 500 mg dose); 500 mg/day or placebo.		
	Study drug doses administered on Days 2, 3,		
	and 4 in a double-blind fashion.		
	Clavulanic acid 750 mg/day dose will always		
	be given on Study Day 5 in a single-blind		
	fashion if both the low and medium doses are		
	well tolerated.		
Duration of Administration	6 day inpatient study, acute oral dosing of		
	CLAV 250 mg/day, 500 mg/day, 750 mg/day		
	and matching placebo		
Reference Therapy	Placebo		
Statistical Methodology	Data are gathered from a 3 period, 3 treatment		
	crossover design (except 750 mg dose). Our		
	primary analyses compare the rates of		
	occurrences of adverse events across the first		
	three periods (250 mg, 500 mg, placebo) within		
	each person using standard mixed effects		
	ANOVA models for binary responses.		

3 MODEL STUDY SCHEMA

4 ABSTRACT

STUDY OBJECTIVES: This is a human laboratory clinical pharmacology study to assess potential interactions between intravenous cocaine and treatment with clavulanic acid (CLAV).

Primary: The primary objective of this study is to determine if there are significant interactions between CLAV treatment concurrent with i.v. cocaine infusions of 40 mg by measuring the frequency of adverse events and cardiovascular responses [heart rate (HR), blood pressure (BP), and electrocardiogram (ECG)] in adult subjects with cocaine use disorder.

Secondary:

- 1. To evaluate whether the acute administration of CLAV alters the pharmacokinetics (PK) of cocaine or its major metabolite, benzoylecgonine (BE) in adult subjects with cocaine use disorder.
- 2. To determine PK of CLAV in adult subjects with cocaine use disorder during treatment at 250 mg/day (low dose) and 500 mg/day (medium dose).
- 3. To evaluate whether there are significant pharmacodynamic (PD) interactions between CLAV treatment (250 mg, 500 mg) concurrent with i.v. cocaine infusions of 40 mg by measuring the diameter of the pupil using a pupillometer.

Exploratory:

- 1. To evaluate whether CLAV treatment alters the subjective effects of cocaine measured by Visual Analog Questionnaire (VAQ) and the Visual Analog Scales (VAS), the perceived value of the dose of cocaine measured by the Drug Value Questionnaire (DVQ), and craving measured by Cocaine Craving Questionnaire-Brief (CCQ-Brief).
- 2. To assess the effects of clavulanic acid on mood and personality using the Profile of Mood States (POMS) and on the abuse liability using the Addiction Research Center Inventory (ARCI).
- 3. To evaluate the safety of CLAV treatment concurrent with iv cocaine infusions with subjects with combined cocaine and opiate use disorder whose opiate use disorder symptoms are stabilized on buprenorphine plus naloxone.
- 4. To evaluate the safety and whether there are significant PD interactions between CLAV treatment 750 mg concurrent with i.v. cocaine infusions of 40 mg.

STUDY ENDPOINTS:

Primary endpoint: Safety and toleration as assessed by the **rates of occurrence of adverse events across the three study periods within each subject.** In addition, the following cardiovascular measures will be assessed during the three study periods: supine vital signs measurements (BP, HR) and ECG standard 12-lead monitoring (QTc prolongation).

Secondary endpoints:

1. PK of cocaine alone will be compared statistically with PK when both Cocaine and CLAV (250 mg, 500 mg) are present. Both the PK of cocaine and its major metabolite,

BE, will be evaluated with both doses of CLAV. PK will be sampled close to T_{max} and drug levels during combination therapy will be compared with drug levels during treatment with each drug alone.

- PK of CLAV alone will be compared statistically at both doses of CLAV (250 mg, 500 mg) PK will be sampled close to T_{max}. If possible, important gender differences in CLAV PK will be explored.
- 3. *PD. Pupil diameter* (over time) after Cocaine infusion alone (with PBO) will be compared with pupil diameter (over time) after Cocaine infusion with CLAV at both doses (250 mg, 500 mg).

Exploratory:

- Subjective effects of cocaine alone (PBO) will be compared with subjective effects of cocaine and CLAV (250 mg, 500 mg, 750 mg) using both the Visual Analog Questionnaire (VAQ) and the Visual Analog Scales (VAS) for each condition (COC+PBO vs. COC+CLAV). The perceived value of cocaine alone (PBO) will be compared with the perceived value of cocaine in combination with CLAV (250 mg, 500 mg, 750 mg) using the Drug Value Questionnaire (DVQ) for each condition (COC+PBO vs. COC+CLAV). Cocaine craving associated with cocaine alone (PBO) will be compared with the craving associated with cocaine alone (PBO) will be compared with the craving associated with cocaine alone (PBO) will be compared with the craving associated with cocaine alone (PBO) will be compared with the craving associated with cocaine alone (PBO) will be compared with the craving associated with cocaine alone (PBO) will be compared with the craving associated with cocaine alone (PBO) will be compared with the craving associated with cocaine alone (PBO) will be compared with the craving associated with cocaine alone (PBO) mg, 750 mg) using measured by Cocaine Craving Questionnaire-Brief (CCQ-Brief).
- 2. *The subjective effects of clavulanic acid without cocaine* (250 mg, 500 mg, and 750 mg) on mood and personality will be assessed using the Profile of Mood States (POMS) score for each dose of CLAV compared with the score on PBO. The effects of CLAV on the abuse liability using the Addiction Research Center Inventory (ARCI) will be compared at each dose of CLAV (250 mg, 500 mg, and 750 mg) compared with PBO score.
- **3.** Safety of clavulanic acid and buprenorphine in combination with cocaine. Safety and toleration as assessed by the rates of occurrence of adverse events across the three study periods within each subject with comorbid cocaine and opiate use disorder. In addition, the following cardiovascular measures will be assessed during the three study periods: supine vital signs measurements (BP, HR) and ECG standard 12-lead monitoring (QTc prolongation).
- 4. Safety of 750 mg clavulanic acid dose. Safety and toleration as assessed by the occurrence of adverse events compared with adverse events on placebo. In addition, the following cardiovascular measures will be assessed and compared with placebo: supine vital signs measurements (BP, HR) and ECG standard 12-lead monitoring (QTc prolongation).

STUDY DESIGN: This is a randomized, double-blind, placebo-controlled inpatient cross-over study of CLAV for Cocaine Use Disorder (CUD). The crossover study will involve acute oral administration of two (2) doses of CLAV (250 mg/day; 500 mg/day); (low and medium) and matched oral placebo in 12 (12 completers, 21 enrolled) healthy non-treatment seeking CUD adult subjects for each drug. The study is performed in an inpatient medical unit (Centennial 6)

at Temple-Episcopal Hospital (T-EH) to determine the safety of the CLAV in combination with cocaine (COC).

STUDY DURATION: Study duration will include up to six (6) days on an inpatient unit in addition to the pre-intake screening and follow up visit. The pre-intake screening will last up to 30 days. The inpatient period will include:

- One (1) outpatient day of intake and admission screening (Day # -30 0)
- One (1) inpatient day of screening cocaine infusions (Day #1)
- Four (4) days of inpatient treatment with CLAV or placebo with i.v. cocaine infusions of 40 mg (Days #2 through #5)

Clinic discharge is on Day #6 unless subject safety precludes them from completing Study Day #5. Liver function test results, hematology studies, CPK results, vital signs, and occurrence/severity of adverse events (AEs) will be reviewed after Study Day #4 to determine eligibility for Study Day #5 at 750 mg.

Subjects will be requested to return for follow-up at 5-8 days after the day of discharge. If subjects have a positive urine for cocaine on inpatient admission, they have the option of being admitted for observation for 24 hours and commencing Study Day #1 on the next day. Subjects with severe cocaine use disorders have difficulty not using cocaine in their community to obtain a negative urine for cocaine. Subjects with combined cocaine and opiate use disorder must have a positive urine test for buprenorphine on admission and a negative test for other opiates to be eligible for Day #1 screening that day. Subjects with a positive test for buprenorphine as well as other opiates will be evaluated on a case by case basis for commencing Study Day #1 after being observed for 24 hours in the hospital.

SAMPLE SIZE: Twenty-one (21) subjects are estimated to enroll, with 12 expected to complete the study. Study subjects who complete the inpatient phase of the study will be considered completed subjects. Subjects will continue to be screened until the total number (n=12) have completed the study.

POPULATION: Volunteer experienced cocaine users, 18-to-65 years of age, who have used cocaine by the smoked or i.v. route at least twice a week for at least four (4) of the past six (6) weeks and provided a positive urine test for cocaine within two weeks of entering the study.

TREATMENTS: The initial crossover study will involve acute oral administration of 2 doses of CLAV (250 mg/day; 500 mg/day); (low and medium) and matched oral placebo. Subject will potentially have four (4) cocaine infusions after randomization, one with CLAV 250 mg, one with CLAV 500 mg (always given after 250 mg dose) and one with placebo (See Figure 1). If subjects tolerate the low and medium dose of cocaine with mild adverse effects, have stable vital signs and bloodwork results that indicate it is safe for them to proceed, they are given 750 mg/day dose on study day #5 on a single blind basis. Subjects will be randomized after the screening cocaine infusion of 40 mg i.v. (Day #1) to one of the following arms:

Treatment Arm 1: Day #2: CLAV 250 mg (low dose); Day #3: CLAV 500 mg; Day #4: Placebo; Day #5: CLAV 750 mg.

Treatment Arm 2: Day #2: CLAV 250 mg (low dose); Day #3: Placebo; Day #4: CLAV 500 mg; Day #5: CLAV 750 mg.

*Treatment Arm 3*: Day #2: Placebo; Day #3: CLAV 250 mg (low dose); Day #4: CLAV 500 mg; Day #5: CLAV 750 mg.

Study	Infusion	Study	Infusion		
Phase	Number	Day			
Screening	Safety	1	Single-blind infusion of COC 20 mg IV		
Stage II	Infusion #1				
Screening	Safety	1	Single-blind infusion of COC 40 mg IV at least 2 hours		
Stage II	Infusion #2		45 minutes after initial infusion		
Treatment	Treatment	2	Single-blind infusion of COC 40 mg IV 60 minutes post		
	Infusion #1		CLAV/placebo administration		
Treatment	Treatment	3	Single-blind infusion of COC 40 mg IV 60 minutes post		
	Infusion #2		CLAV/placebo administration		
Treatment	Treatment	4	Single-blind infusion of COC 40 mg IV 60 minutes post		
	Infusion #3		CLAV/placebo administration		
Treatment	Treatment	5	Single-blind infusion of COC 40 mg IV 60 minutes post		
	Infusion #4		single-blind CLAV 750 mg administration		

Table 1.	Cocaine	Infusion	Session	Schedule

STATISTICAL ANALYSIS PLAN

5.1 Outcome Measures

5.1.1 Primary Outcome Measures

The primary outcome measures are adverse events and cardiovascular responses (HR, BP, ECG (QTc prolongation). Safety and toleration as assessed by the **rates of occurrence of adverse** events across the three study periods (250 mg, 500 mg, PBO) within each subject.

5.1.2 Secondary Outcome Measures

Secondary outcome measures are intended to determine if there are any changes in cocaine pharmacokinetics in the presence of clavulanic acid (250 mg, 500 mg) after acute dosing of

CLAV. The pharmacokinetics of clavulanic acid at 2 doses (250 mg, 500 mg) will be determined in non-treatment seeking adults with cocaine use disorder. The pharmacodynamic effects of clavulanic acid in combination with cocaine will be determined by measuring the diameter of the subject's pupil after the cocaine infusion.

5.1.3 Exploratory Outcome Measures

Exploratory outcome measures are intended to evaluate whether if there are any changes in the subjective effects of cocaine in the presence of clavulanic acid (250 mg, 500 mg, 750 mg) after acute dosing of CLAV. The subjective effects of clavulanic acid without cocaine in non-treatment seeking adults with cocaine use disorder will be assessed at all doses (250 mg, 500 mg, 750 mg).

5.2 Data Analysis Plan

5.2.1 Primary Outcome Measures

The primary objective of this study is to assess the safety and tolerability of CLAV in combination with cocaine to generate data regarding the safety of the combination of CLAV and cocaine in relevant doses of both drugs. This is required prior to an outpatient efficacy study of CLAV for cocaine use disorders. Secondary objectives are to assess whether cocaine alters serum levels of CLAV and to assess serum levels of CLAV at both doses of CLAV in study subjects. Exploratory objectives are to assess the subjective ratings of drug effects with regard to craving and mood. Summary statistics will be provided for all safety, tolerability and subjective data. In addition to the analyses specified below, listings of all data for each patient will be provided.

5.2.1.1 Demographic and Baseline Comparability Analyses

Demographic variables will be summarized for all for male and female patients.

5.2.1.2 Primary, Secondary, and Exploratory Analyses

5.2.1.2.1 Primary Analyses: Safety is a primary assessment variable. The number of patients reporting each AE by treatment group and severity will be presented. Adverse events will be tabulated by body system and organ class. In addition, all adverse events (AE's) noted during the study will be listed. The listings will include each occurrence of the AE, when it was reported, the severity and the duration. Adverse event data will be compiled for CLAV at all doses (250 mg, 500 mg, 750 mg) and placebo and presented as summary statistics by organ system. Our primary analyses will compare the rates of occurrence of adverse events across the three-periods within each person. The data are gathered using a 3-period 3-treatment crossover design. Safety concerns constrain us to restrict the order of administration of the 2 study drug doses of CLAV, so each subject receives the doses in increasing order. Thus, we have three sequences: {PBO, Low (250 mg), Medium (500 mg)}, {Low, PBO, Medium}, and {Low, Medium, PBO}. One third of the subjects are randomized to each of these sequences. Each period is a 1 day session and the periods correspond to days 2, 3, and 4, providing 24 half-lives between administrations. The main explanatory variables in the models are: 1) a 3 level within-

subject factor representing drug condition (PBO, study drug low dose (SDlow), study drug medium dose (SDmedium), and 2) a three level factor representing period (1, 2, and 3). We use standard mixed effects (repeated measures) ANOVA models for binary responses in three-period three-treatment crossover designs to test our hypotheses.⁷³ An overall F-test of the condition effect will test for differences in response across the three drug doses, and contrasts will determine the pattern of differences (if any). Mixed effects models can allow for different error variances for different sessions, and other complex error structures as needed. As this study has only three repeated measures, a relatively simple covariance structure model (e.g. heterogeneous compound symmetry model) should be sufficient to account for within-subject correlations.

Pharmacodynamic parameters (systolic and diastolic blood pressure, heart rate and QT_C interval, expressed as AUC, 2-minute values and maximal values) will be similarly analyzed. The COC infusions occur on the day of each session, providing three repeated sets of measures of each COC related response (change in HR, change in SBP, change in DBP, change in QT_c interval,).

HR and BP (systolic BP (SBP) and diastolic BP (DBP)) and QT_C induced by cocaine infusion will be compared to HR and BP and QT_C measurements before the cocaine infusion to assess change. BP and HR and QT_C changes after infusion given after CLAV (250 mg, 500 mg, 750 mg) will be compared to those without CLAV. We will compare the distribution of Area Under Curve (AUC) summaries of the within-period repeated measures of changes in vital signs (heart rate, systolic blood pressure, diastolic blood pressure) across the three-periods within each person as described above.

 QT_C interval measured by the ECG induced by cocaine infusion will be compared to QT_C interval before the cocaine infusion to assess change. QT_C interval changes after infusion given after CLAV (250 mg, 500 mg, 750 mg) will be compared to those without CLAV. We will compare the distribution of Area Under Curve (AUC) summaries of the within-period repeated measures of changes in QTc interval across the three-periods within each person as described above.

5.2.1.2.2 Secondary Analyses: The pharmacokinetic parameters will be statistically analyzed using a repeated measure analysis of variance model.

5.2.1.2.3 Exploratory Analyses: Subjective effects of cocaine, as measured by check lists, visual analog and rating scales, will be listed for each patient and summarized for each group. Adverse events for the CLAV 750 mg group will be analyzed as described above for the lower CLAV doses. Adverse events for the subset of subjects stabilized on Buprenorphine will be analyzed as described above.

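### The only inferential adverse-event analysis is an F-test with contrasts in about 12 completers; no interval for excess AE risk over placebo is planned

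*Combined protocol and SAP*

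**What the plan says.** Section 5.2.1.2.1 makes the AE comparison primary: "Our primary analyses will compare the rates of occurrence of adverse events across the three-periods within each person". The model has a three-level condition factor (placebo, 250 mg, 500 mg) and a three-level period factor, and is described as follows: "We use standard mixed effects (repeated measures) ANOVA models for binary responses in three-period three-treatment crossover designs to test our hypotheses". Inference is then in two steps: "An overall F-test of the condition effect will test for differences in response across the three drug doses", after which "contrasts will determine the pattern of differences (if any"). The order of treatments is only partly randomised: "Safety concerns constrain us to restrict the order of administration of the 2 study drug doses of CLAV". One third of subjects go to each of three sequences.

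The same section also plans descriptive output: patients with each AE by treatment and severity, tables by organ class, and full listings. Heart rate, blood pressure and QTc get their own analyses.

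Section 4 (Sample size) gives 12 completers and about 21 enrolled, without an AE rate, effect size, alpha or power. Section 5.2.1 gives the purpose of the safety data: "This is required prior to an outpatient efficacy study of CLAV for cocaine use disorders".

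**The concern.** The safety question is how much the AE risk could rise when CLAV is added to cocaine. An F-test asks only whether some difference can be detected. With about 12 subjects, a non-significant F can occur when the true excess is zero and also when it is 20 or 30 points. An estimate with an interval separates these cases, but the plan promises none for AEs.

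It is also unclear what scores 1 in a session: any AE, each AE term, or AEs above some severity. Every session includes an IV cocaine infusion ("The COC infusions occur on the day of each session, providing three repeated sets of measures of each COC related response"), so this choice could move the event rate from low to high. If it stays open, it will be made after the data are seen. On its own that is missing detail, but no interval can be computed until it is settled.

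At stake is what the trial can say about AE risk to those planning the outpatient study.

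**Working it through.** **Inputs from the documents.** 12 completers, 21 estimated to enroll (section 4). Three sequences, equally allocated: placebo-250-500, 250-placebo-500, 250-500-placebo (section 5.2.1.2.1). Three sessions per subject.

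**Assumptions.** AE rates per session of 10% to 70%; two-sided alpha 0.05; between-subject SD of 0, 1 or 2 on the logit scale, with the marginal rates held fixed. The test is a linear model with subject, period and condition, standing in for a binary mixed model whose link is not stated. The plan has no AE power or precision figure to reproduce.

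**Step 1: precision of a dose-versus-placebo contrast.** Without period, the variance is 2/12 = 0.167 times the within-subject variance. With period in the model and the restricted sequences it is 0.200, a ratio of 0.200/0.167 = 1.20. Residual degrees of freedom are 36 − 12 − 2 − 2 = 20, so t = 2.086. For independent responses at rate p, the within-subject variance is p(1−p), and the 95% half-width is about 2.086 × √(0.200 × p(1−p)):

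- p = 10%: 2.086 × √0.018 = 28 points
- p = 30%: 2.086 × √0.042 = 43 points
- p = 50%: 2.086 × √0.050 = 47 points

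The simulated median half-widths over SD 0 to 2 agree: 23-27 points at 10%, 29-37 at 20% and 33-43 at 30%.

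**Step 2: power of the overall F-test (2 and 20 df), n=12.**

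| Placebo/250/500 mg | Power over SD 0 to 2 |
|---|---|
| 10/20/30% | 11-15% |
| 10/20/40% | 24-31% |
| 20/30/50% | 21-28% |
| 30/40/60% | 20-27% |
| 40/50/70% | 20-28% |
| 10/30/60% | 58-74% |

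If all 21 enrolled subjects supplied every session, which is an upper bound, power for the +10/+30 rows would be 34-61%. Type I error is acceptable, at 3-5% for rates of 10-50%.

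**Step 3: what a non-significant F leaves open.** With no true effect and a non-significant F at n=12, the share of trials in which the 95% upper limit for 500 mg minus placebo reaches +20 points is:

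| Common AE rate | Share of trials |
|---|---|
| 10% | 55-68% |
| 20% | 72-83% |
| 30% | 78-87% |
| 50% | 80-89% |

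**Step 4: the paired score interval at 12 pairs.** With no discordant subject the limits are ±z²/(n + z²) = 3.84/15.84, so 0 (−24 to +24 points). With 3 subjects having an AE on CLAV only and 1 on placebo only: +17 (−19 to +49), exact McNemar p = 0.63. With 3 against 0: +25 (−5 to +53). An exact McNemar test needs at least 6 discordant subjects, all in one direction, to fall below 0.05: 2 × 0.5⁶ = 0.031, while 2 × 0.5⁵ = 0.0625.

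**The case against.** The strongest reply is that this is a small Phase 1 study whose safety reading is mainly descriptive. The tables, listings and cardiovascular analyses lose nothing, and paired counts can be taken from the listings. That is true, and it limits the point to AE inference. But the plan itself chose a hypothesis test as the primary AE analysis, and anyone deriving intervals later must first choose the response.

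A second reply is that contrasts from a mixed model normally come with an estimate and standard error. This also stands: intervals are not excluded. They are not committed to either, and the contrasts are assigned only to finding a pattern of differences.

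Four stronger readings are tempting, and the documents do not support them:

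- *Power is low whatever the truth.* It depends on the size of the excess: 10/30/60% gives 58-74% at n=12. The weakness concerns small to moderate excesses.
- *The sponsor will treat a non-significant F as proof of safety.* No section says so.
- *Early stoppers will be lost and the AE comparison biased.* Completion is defined in section 4 as a recruitment target, and no section restricts the AE comparison to completers. The statement "Clinic discharge is on Day #6 unless subject safety precludes them from completing Study Day #5" concerns the 750 mg day, outside the three-period comparison. A mixed model can use the sessions that are available.
- *The model will fail to give finite estimates.* That needs a logistic link and an uncommon response, and the plan states neither.

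**Conclusion.** The point holds for AE inference only. The plan commits to a test that would usually miss an excess of 20 to 30 points at 500 mg, and to no statistic that shows what excess is still compatible with the data. When the F is non-significant and there is no true effect, an upper limit of +20 points or more is the usual outcome at AE rates of 10% and above.

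The figures rest on assumed AE rates, a two-sided 5% level, a linear stand-in for the unspecified binary model, and 12 subjects with complete data. The direction is the same at every between-subject SD tried, and it persists for the +10/+30 excesses at 21 complete subjects. The change is worth making because it alters what the trial can conclude on the question in section 5.2.1 and needs only wording.

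**What to change.** In section 5.2.1.2.1, keep the planned model and add:

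1. The 0/1 response per session, for example any AE, with any moderate-or-worse AE as supportive.
2. As the lead result, for 250 mg and for 500 mg versus placebo, the period-adjusted within-subject risk difference with its 95% interval, from all dosed sessions.
3. As supportive, the score-based 95% interval for paired proportions. It is the only interval when the model has no residual variance, for example when no session has an AE.
4. A statement that the AE conclusion rests on these estimates and limits and not on a non-significant F-test. Report both intervals side by side, with no rule that labels a disagreement inconclusive, because such a rule could downgrade a signal.

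The 750 mg and buprenorphine AE analyses in section 5.2.1.2.3 borrow this method, so the definition of the response will clarify them too.

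**Cost.** SAP wording and standard software; design, dosing and sample size do not change. There are four drawbacks:

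- The intervals will be visibly wide, with median half-widths of about 23-27 points at a 10% rate and 33-43 at 30%.
- The paired interval uses only subjects with both sessions and is not period-adjusted. If rates fell 20/15/10% over Days 2 to 4, it would shift by (20+20+15)/3 − 15 = +3.3 points for 250 mg and (15+10+10)/3 − 15 = −3.3 for 500 mg.
- At small counts it can disagree with an exact test: 4 against 0 gives a lower limit of +1 point but McNemar p = 0.125.
- The model-based interval has zero width in 16-25% of trials at a 5% rate and 2-8% at 10%, which is why the score interval is needed as well.

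The change sets no tolerable excess, since the documents give none; readers would judge the limits themselves.

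### The only hypothesis test on adverse events uses a yes/no response, so it cannot detect CLAV making cocaine's adverse events more severe, and it weakens if most cocaine-plus-placebo sessions already contain an event

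*Combined protocol and SAP*

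**What the plan says.** The primary AE comparison is within subject, over placebo, 250 mg and 500 mg (5.2.1.2.1): "Our primary analyses will compare the rates of occurrence of adverse events across the three-periods within each person". The model is for a yes/no outcome: "We use standard mixed effects (repeated measures) ANOVA models for binary responses in three-period three-treatment crossover designs". The test is specified as follows: "An overall F-test of the condition effect will test for differences in response across the three drug doses". Contrasts follow, and period is also in the model. The remark "As this study has only three repeated measures" implies one response per session. The plan does not say whether that response is any AE in the session or each AE type in turn.

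Severity is collected and reported descriptively: "The number of patients reporting each AE by treatment group and severity will be presented", and "The listings will include each occurrence of the AE, when it was reported, the severity and the duration". No test uses it. Section 5.2.1.2.3 carries the same AE method over to the 750 mg dose and to the buprenorphine subset.

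Table 1 (Cocaine Infusion Session Schedule) puts a 40 mg i.v. cocaine infusion in every treatment session. BP, HR and QTc are also primary and are analysed as AUC, 2-minute and maximal values.

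**The concern.** The comparator is cocaine alone, not an event-free baseline. The Synopsis asks about clinically significant adverse interactions, and one central form of interaction is that CLAV makes cocaine's own adverse effects worse. A yes/no response has two weaknesses here.

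- It is blind to a change in severity that leaves occurrence unchanged. A mild event and a severe event both score 1.
- If cocaine alone often produces an AE, an any-AE response is already near its ceiling on placebo days and has little room to rise on CLAV days.

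At stake is a non-significant primary AE test being read as reassurance before the planned outpatient efficacy study, when the test could not have responded to the change of interest.

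**Working it through.** **The plan's own figure.** The sample size ("Twenty-one (21) subjects are estimated to enroll, with 12 expected to complete the study") comes with no alpha, power, effect size or AE rate, so there is no power figure to reproduce.

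**Inputs from the documents.** 12 completers; three sequences ("One third of the subjects are randomized to each of these sequences", so 4 subjects each); subject, period and condition terms. Residual degrees of freedom: 12 × 3 − 12 (subjects) − 2 (period) − 2 (condition) = 20, so the condition F-test has 2 and 20 df.

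**Assumptions (not in the documents).** Two-sided alpha 0.05; subject SD of 1 on the logit scale; common log-odds shift of 1.5 at both doses and at every severity cut-point; grades 0 none, 1 mild, 2 moderate, 3 severe. Placebo-session probabilities of (any, moderate or worse, severe) are (.50, .20, .05), (.70, .30, .08), (.85, .40, .10) and (.95, .50, .12). The same F-test was applied to any AE (0/1) and to worst grade (0-3). The linear score stands in for an ordinal model, so exact figures would move somewhat under another model.

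**Power under the common shift.** Relative loss = (worst grade − any AE) / worst grade.

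| Placebo AE rate | Any AE | Worst grade | Relative loss |
|---|---|---|---|
| 50% | 34% | 44% | 10/44 = 23% |
| 70% | 27% | 46% | 19/46 = 41% |
| 85% | 14% | 45% | 31/45 = 69% |
| 95% | 3% | 44% | 41/44 = 93% |

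A separate run of 3,000 trials per setting gives 36 vs 45, 26 vs 46, 14 vs 45 and 2 vs 43%. Null rejection is 2-5% for any AE and 4-6% for worst grade. Linear interpolation between 70% and 85% puts the relative loss at 80% at about 41 + (10/15) × (69 − 41) = 60%.

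**A second model** (latent normal; shifts of 0.5/1.0 or 0.75/1.5 SD at 250/500 mg; within-subject correlation 0.3-0.7; 70-95% of AEs mild) gives relative losses of 23-51% at a 60% rate, 30-61% at 70%, 39-75% at 80%, 51-82% at 85% and 64-91% at 90%.

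**Severity worsens, occurrence unchanged.** Any AE rejects in 2-5% of trials, which is its null rate. Worst grade rejects in 19%, 26% and 36% at placebo rates of 70%, 85% and 95%. The second model gives 24-82% for the severity score at 80-95% (70% of AEs mild, correlation 0.3-0.5).

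**Where the loss shrinks or reverses** (log-odds model, any AE vs worst grade).

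- Only 10% of AEs moderate or worse: 34 vs 37% at a 50% rate, 26 vs 32% at 70%, 14 vs 26% at 85%. The last is a loss of 12/26 = 46%.
- Low rates: 16 vs 12% at 10%, 28 vs 25% at 20%, 34 vs 34% at 30%.
- CLAV adds new mild AEs only (assumed 60% chance per CLAV session, no worsening): 59 vs 32% at 30%, 48 vs 24% at 40%, 37 vs 17% at 50%.

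**The case against.** Four points on the other side carry weight.

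- **The ceiling is conditional.** The documents give no cocaine-plus-placebo AE rate. If AEs are uncommon, occurrence does as well as worst grade or slightly better. The main table's grade splits put 40% (.20/.50) to 53% (.50/.95) of AE sessions at moderate or worse, which favours a severity score. This stands, and it limits the size of the loss.
- **The response may be per AE type.** Each type would then have a lower placebo rate and a milder ceiling, so the quoted losses need not apply. This stands for the losses. It does not rescue the test from missing a change in severity alone.
- **Severity is not lost, and other primary measures cover part of the question.** A reader might infer that the trial discards severity, or that worsening of cocaine's effects would go unseen. The documents do not support that: severity is tabulated by treatment and listed per event, and BP, HR and QTc are analysed as graded measures with no 0/1 ceiling. What remains untested is worsening of AEs outside those measures.
- **Worst grade is not uniformly better.** It loses clearly if CLAV mainly adds new mild events, and even in its favourable setting its power is only about 45%. This stands, and it argues against replacing occurrence.

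**Conclusion.** The concern holds in a limited form. The blindness to a severity-only change follows from the definition of the response and needs no assumption about rates. The loss of power applies if the response is any AE in the session: about a fifth at a 50% placebo AE rate, about 40% at 70%, and more than half from roughly 80%. Those figures rest on the 1.5 log-odds shift and the assumed grade splits. With mostly mild AEs the loss is smaller and in the log-odds model stays just under half even at 85%; at rates of 30% or below there is none.

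A reader might infer that the test loses most of its power as soon as cocaine alone causes an AE in most sessions. That is too strong. At a bare majority the relative loss is roughly a quarter to a half in the second model and less in the first, and the documents do not say that AEs on cocaine alone are that common. The point merits a change because the trial's own question includes worsening of cocaine's effects and the needed data are already recorded.

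**What to change.** Keep the occurrence comparison and state whether its response is any AE in the session or each AE type. Beside it, prespecify an inferential analysis of each subject's worst AE severity per session (0 none, 1 mild, 2 moderate, 3 severe), with the same subject, period and condition terms. Use either a cumulative-logit mixed model or linear scores with a p-value from re-randomising subjects to the three sequences. Report both results, and retain the severity tables and listings.

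The cost is SAP wording and one more model, with no new data. The added analysis relies on investigator grading and on an ordinal assumption. It has less power than occurrence if CLAV mainly adds new mild AEs, which is why occurrence should not be demoted.
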